11.2. Medications

Information regarding drugs prescribed to treat atrial arrhythmias will be collected, including the purpose for their use/reason for modification, and start and stop dates. Information regarding anticoagulation medications will be collected, including start and stop dates.

Control Arm (AAD): Subjects must initiate a Class I or III AAD within 30 days of randomization. It is recommended that AADs be initiated as soon as possible after randomization, with a target of within 14 days. The investigator should choose the appropriate AAD per his or her standard of care; however, amiodarone should only be used if other AADs were not tolerated or failed. The 2014 AHA/ACC/HRS

⁴ Subjects shall submit ECG transmissions weekly and whenever symptoms occur after the AAD optimization/post-ablation blanking periods through 12 month follow-up.

Guideline for the Management of Patients with AF should be consulted for AAD prescriptions. Modifications to AADs (type or dosage increase) may be made for up to 90 days after AAD initiation. This is referred to as the AAD optimization period. Dosing of AADs can be individually tailored until the end of the AAD optimization period. After the optimization period, further AAD therapy optimization or change should be avoided or at least allowed only up to physicians' discretion to guarantee the safety of the patients. The possible concomitant use of beta blockers can still be optimized after the optimization period.

Treatment Arm (Cryoablation): Subjects may be prescribed Class I or III AADs for up to 80 days post-ablation procedure at the discretion of the Investigator. Subjects must stop taking all Class I or III AADs before day 81 post-ablation. Use of amiodarone is not permitted.

Anticoagulation requirements for all subjects:

Anticoagulation pre-procedure should be determined based upon the subjects CHA₂DS₂-VASc score.

- a. Oral anticoagulants are required if the subject has had a prior stroke or TIA, or if the subject has a CHA₂DS₂-VASc score ≥ 2 . When anticoagulation is required, subjects must take it for at least 21 days prior to an ablation procedure.
- b. Oral anticoagulants are not required for subjects with nonvalvular AF and a CHA₂DS₂-VASc score of 0 or 1.

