11.4. Randomization and Treatment Assignment

Enrolled subjects are eligible for randomization after all inclusion and none of the exclusion criteria are met and after the baseline QoL questionnaires are completed. Subjects will be randomized in a 1:1 fashion to undergo a cryoablation procedure (treatment arm) or receive AAD therapy (control arm).

See Section 11.5.2 for control arm procedures and Section 11.5.3 for treatment arm procedures.

Subjects will be randomized using an electronic randomization system. The randomization schedule will be stratified by study site to ensure that within each study site randomization is approximately 1:1.

Subjects will be analyzed according to a modified intention-to-treat protocol: subjects who withdraw their informed consent prior to the index cryoablation procedure or initiation of AAD therapy will be excluded from the analysis of the primary safety and efficacy endpoints. Otherwise, the standard intention-to-treat protocol is applied: subjects who receive either therapy, regardless of what it actually is, will be analyzed according to their randomization status. This allows for the protection of the benefits of randomization, while avoiding the problem of attrition and adverse events occurring in the time between randomization and the initiation of treatment, which, due to the practicality of scheduling can be up to 30 days. All randomized subjects should be encouraged to comply with the study procedures until study closure.

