11.10. Subject Withdrawal or Discontinuation

A subject can withdraw from the study at any time. If the subject wishes to exit from the study (i.e. the subject revokes consent), the center is required to document the reason for exit on an eCRF. In addition, centers shall follow the regulations set forth by their IRB/EC.

Prior to exiting a subject from the study, it is recommended to follow the subject until all ongoing device and/or procedure related adverse events are resolved or unresolved with no further actions planned. An unscheduled office visit should be attempted if the subject exits the study outside of a scheduled follow-up visit.

Following exit, subjects will continue to receive standard medical care. Upon exiting from the study, no further study data will be collected or study visits will occur for the subject. All data available through the time of the subject's exit will be used for analysis.

Reasons for subject withdrawal or discontinuation include:

- Subject is lost to follow-up
- Subject did not meet inclusion/exclusion criteria after the date the subject signed the Informed Consent Form and prior to randomization.
- The subject was randomized to the treatment arm, but no cryoballoon ablation procedure was attempted
- The subject was randomized to the control arm, but no AAD was initiated
- Subject chooses to withdraw (e.g., Informed Consent Form withdrawal, relocation to another geographic location)
- Investigator deems withdrawal necessary (e.g., medically justified, inclusion/exclusion criteria not met, failure of subject to maintain adequate study compliance)
- The sponsor or regulatory authority decides the study will be closed or a particular center will be closed

The following information is required to be collected at early study exit:

- Reason for exit must be documented on the eCRF and in the subject's medical record
- An unscheduled office visit should be attempted if the subject exits the study outside of a scheduled follow-up visit

In the case that the subject is determined to be lost to follow-up, details of a minimum of two attempts and the method of attempt (e.g., one letter and one phone record or two letters) to contact the subject must be recorded. In addition, follow the regulations set forth by the governing IRB/EC.

12. Risks and Benefits

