13.2. Reporting of Adverse Events

For the purposes of this study, the following Adverse Events will be collected starting at the time the subject signs the Informed Consent Form through the duration of the subject's participation in the study:

- All procedure related AEs
- All cryoablation system related AEs
- All AAD related AEs
- All cardiovascular related AEs
- All Serious Adverse Events (SAEs), regardless of relatedness

Reporting of these events to Medtronic will occur on an Adverse Event (AE) Form, including a description of AE, date of onset of AE, date of awareness of site, treatment, resolution, assessment of both the seriousness and the relatedness to the investigational device.

Each AE must be recorded on a separate AE Form. Exceptions include:

- Documented pre-existing conditions are not considered AEs unless the nature or severity of the condition has worsened. Additionally, arrhythmia episodes that are not new or worsening conditions and for which no action is taken are not reportable as AEs.
- Unavoidable Adverse Events, listed in section 13.1 need not be reported unless the adverse event worsens or is present outside the stated timeframe post-procedure.
- Cardioversions (DC or Drug) for recurrent symptomatic atrial fibrillation and other atrial arrhythmias are not considered serious adverse events.

For any changes in status of a previously reported adverse event (i.e. change in actions taken, change in outcome, change in relatedness), an update to the original AE must be provided. All adverse events must be followed until the adverse event has been resolved, is unresolved with no further actions planned, the subject exits the study or until study closure, whichever occurs first.

In the event that a subject is exited from the study prior to study closure, all efforts should be made to continue following the subject until all unresolved procedure or cryoablation system related adverse events, as classified by the investigator, are resolved or they are unresolved with no further actions planned.

At the time of study exit, all adverse events with an outcome of "Unresolved, further actions or treatment planned" must be reviewed and an update to the original AE must be reported. At a minimum, if there are no changes to the description, relatedness, test and procedures or actions taken, the outcome must be updated to reflect "Unresolved at time of study closure."

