### 6.2.2.4. Analysis Methods

The probability of a subject achieving success at 12 months (365 days) will be estimated using Kaplan-Meier survival analysis. The standard error will be approximated using Greenwood's formula. A two-sided 95% log-log confidence interval for the probability will be constructed. A log rank test with  $\alpha = 0.05$  will be used to assess whether the failure rate differs between treatment groups.

Day 0 is defined as either the day of the index cryoablation procedure or the day in which AAD drug therapy is initiated. For subjects with treatment failure, the survival date will be set to the date of the treatment failure. For subjects without treatment failure through 12 months, those subjects will be censored at the last study contact date recorded on a CRF, which may include the last study visit, the exit date, or death date. If a subject without a treatment failure is lost to follow-up, the censoring date will be set to the last recorded study visit date. If treatment failure occurs on the day of index treatment, survival time will be set to 0.5 days.

If an occurrence of documented AF/AT/AFL resulted from rhythm monitoring that was initiated at the 12-month visit, then the date of occurrence used in the Kaplan-Meier analysis will be the minimum of 365

days from the cryoballoon ablation procedure/date of AAD initiation, or the actual date of occurrence. This allows counting of all AF/AT/ AFL events found at the 12-month follow-up, even if the follow-up occurred after 365 days post-ablation but still within the visit window. Events found at 12-month visits outside of the window will be censored at the previous follow-up and described in deviation listings.

The survival curves from 0 to 12 months will be presented for both treatment arms.

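### Protocol 11.10 lets an unblinded investigator end follow-up of a treated subject for poor compliance or unmet eligibility, which can produce outcome-related censoring in the primary efficacy analysis

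*Protocol*

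**What the plan says.** Protocol 11.10 lists the reasons for withdrawal or discontinuation. One is "Investigator deems withdrawal necessary (e.g., medically justified, inclusion/exclusion criteria not met, failure of subject to maintain adequate study compliance". It carries no time limit and no sponsor or blinded review. A separate eligibility reason in the same list is limited in time: "Subject did not meet inclusion/exclusion criteria after the date the subject signed the Informed Consent Form and prior to randomization".

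On the data, 11.10 says "All data available through the time of the subject's exit will be used for analysis", and also "Upon exiting from the study, no further study data will be collected or study visits will occur for the subject". An unscheduled visit at exit is to be attempted but is not mandatory. The reason for exit is recorded on the eCRF and in the medical record.

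On analysis, SAP 6.2.2.4 (matching Protocol 15.1.5) has subjects without a treatment failure "censored at the last study contact date recorded on a CRF, which may include the last study visit, the exit date", or the death date. Protocol 11.4 analyses treated subjects in their randomised arm and adds: "All randomized subjects should be encouraged to comply with the study procedures until study closure".

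On drugs in the cryoablation arm, Protocol 11.2 says "Subjects must stop taking all Class I or III AADs before day 81 post-ablation". Under 5.1.4.1, component (e), class I or III drug use after the 90-day blanking period is a treatment failure in that arm.

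On safety after early exit, Protocol 13.2 says "all efforts should be made to continue following the subject until all unresolved procedure or cryoablation system related adverse events" are resolved or need no further action.

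**The concern.** The Kaplan-Meier estimate and the log-rank test assume that a censored subject has the same future risk as those still under observation. Loss to follow-up and relocation may come close to that. Exit for poor compliance may not, because the behaviour that counts as non-compliance can be a sign of a failing treatment. The decision is also made by someone who knows the arm.

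At stake are the size of both success estimates and, if exits are selective in one arm, the error rate of the superiority test. The missing outcomes cannot be reconstructed, because nothing is collected after exit.

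**Working it through.** **The plan's own figures.** For two proportions p1 and p2 with mean p̄, n per arm = [1.960·√(2p̄(1−p̄)) + 1.282·√(p1(1−p1) + p2(1−p2))]² / (p1−p2)². With the SAP 7.1 rates of 69.9% and 45.9%, p̄ = 0.579 and n = (1.3685 + 0.8680)² / 0.0576 = 86.8. That is 87 per arm and 174 in total, and 174/0.9 gives 194 randomised. The safety requirement is 94/0.9 = 105 per arm, hence 210. The sample size is not in dispute. I use 105 per arm below.

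**The chain in the documents.**

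| Step | Source | Content |
|---|---|---|
| Knowledge of arm | Protocol 6 | Unblinded |
| Discretionary exit | Protocol 11.10 | Poor compliance, or eligibility with no time limit |
| Data after exit | Protocol 11.10 | None |
| Handling | Protocol 15.1.5, SAP 6.2.2.4 | Censored if no documented failure |
| Decision rule | Protocol 15.1.3 | Log-rank test alone |

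**A concrete route.** A cryoablation subject still taking a class I or III drug after day 80 is non-compliant with 11.2. If the subject stays in the study and use continues past day 90, component (e) makes this a failure. If the investigator exits the same subject for non-compliance between day 81 and day 90, the subject is censored with no failure recorded.

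**Effect on the estimate (illustration).** Expected cryoablation failures are 0.301 × 105 = 31.6. Suppose k would-be failures leave before any failure has occurred and nobody else is censored. Estimated success is then 1 − (31.6 − k)/(105 − k).

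- k = 1: 1 − 30.6/104 = 70.6%
- k = 3: 1 − 28.6/102 = 72.0%
- k = 5: 1 − 26.6/100 = 73.4%

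The same formula applies to the control arm at 45% success, with 0.55 × 105 = 57.75 expected failures. Five such exits give 1 − 52.75/100, about 47%, and this narrows the difference.

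**Effect on the test (illustration).** I simulated the log-rank test with 105 per arm, both arms truly at 45%, and a constant hazard from day 91 to day 365. Only cryoablation subjects were selectively exited. The false-positive rate in favour of cryoablation has a nominal value of 2.5%.

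| Would-be failures exited | Exit at day 85 | Exit one day before failure |
|---|---|---|
| 0 | 2.6% | 2.4% |
| 3 | about 4% | 4.5% |
| 5 | about 5% | 6.7% |

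With exit one day before failure, ten selective exits from each arm leave this rate near nominal at 2.9%, but both success estimates rise from 45% to about 52%. Five selective exits from the control arm only, at true rates of 69.9% and 45%, lower power from 96.3% to 89.2%.

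**The case against.** The strongest reply is SAP 6.4.1. It plans a tipping-point analysis for subjects who exit before 12 months. Each censored cryoablation subject becomes a failure the day after censoring, and each censored control subject is carried event-free to day 365, until significance is lost. With fewer than five missing, a worst-case analysis replaces it. This is harsher than the scenario above, and it would show whether the result depends on the exits. It does not close the gap. It is a sensitivity analysis outside the success criterion, and it does not supply the lost outcomes. For efficacy it also runs on the full analysis set, which SAP 6.1.3 restricts to subjects who meet the eligibility criteria, so a subject found ineligible late may not be in it.

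Other points stand and limit the concern:

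- Nothing directs an investigator to exit a subject who stays on a drug. Protocol 11.5.5 says such use after the blanking period is an endpoint failure.
- A missed visit is a deviation with the original schedule kept (11.5.8), and SAP 6.1.1 reports withdrawals by arm. The default is retention.
- Acute procedural failures are dated to the index day and cannot be removed by a later exit.

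Some stronger readings are tempting but not supported:

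- A reader might infer that 11.4 requires every randomised subject to continue to closure. It only asks that they be encouraged to comply.
- A reader might infer that the analysis stops being intention-to-treat, or that exited subjects count as successes. They stay in their assigned arm and leave the risk set at exit.
- A reader might take the 11.1–28.1% discontinuation figure in Protocol 4.1 as the share of control subjects exposed to this rule. It is stopping of treatment for adverse events in a cited study. It is neither study exit nor non-compliance.
- A reader might apply the formula to all planned attrition: 10.5 subjects give 1 − 21.1/94.5 = 77.7%. That needs every cryoablation loss to be a would-be failure, whereas the 10% covers attrition of every kind.

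**Conclusion.** The concern holds as a gap in the rules for follow-up. As written, 11.10 permits censoring that is related to outcome and decided with knowledge of the arm, and the planned sensitivity analysis can reveal the effect but not undo it. The documents do not show that this will happen often or that it would favour cryoablation.

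The size is illustrative: a gain of about 2 to 3.5 percentage points in estimated cryoablation success for three to five selective exits. It rests on three assumptions: the number of exits, that all would have failed, and that they left before other failures occurred. The false-positive figures further assume that selective exit occurs in one arm only.

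The wording of 11.10 on data after exit also conflicts with the adverse-event follow-up in 13.2. That conflict is minor, since 11.10 itself recommends following related events before exit, but the two passages must be reconciled. The change should be made before exits occur, because the outcomes cannot be collected afterwards.

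**What to change.** In Protocol 11.10:

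1. Delete poor compliance as a ground for study exit.
2. Limit the unmet-eligibility ground to before randomisation, matching the separate reason already in the list.
3. State that once therapy has started, a subject who is non-compliant, is found ineligible late, or stops or changes study treatment stays on the visit and rhythm-monitoring schedule to 12 months while consent continues. Record deviations only where 11.9 already requires them: it exempts missed ambulatory transmissions, and 11.2 allows for changes of drug in the control arm.
4. Keep medically justified withdrawal available, but collect endpoint data afterwards where the subject still consents.
5. Reconcile the sentence that ends data collection at exit with the follow-up after early exit in 13.2.

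In SAP 6.4.1, run the efficacy tipping-point analysis on all mITT subjects.

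These changes separate stopping or changing treatment from leaving the study, and they leave treatment decisions as they are. The cost is protocol and SAP wording and site training. The downside is that some less compliant subjects will remain in follow-up with sparse recordings.

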12.1. Potential Risks

Medtronic follows rigorous Quality Assurance and Control procedures throughout the life of a product, from the business analysis phase through development, market release, and post-market surveillance. The residual risks associated with the Arctic Front Advance™ Cardiac CryoAblation Catheter have been found to be acceptable and have been mitigated to the fullest extent possible. The potential benefits related to the use of the Arctic Front Advance™ Cardiac CryoAblation Catheter have been determined to outweigh any potential risks. The device has never been recalled.

There are potential risks and side effects associated with Class I and III AADs. A complete list of known risks associated with the drugs used in this study can be found within their approved labeling.

There are potential risks and side effects associated with ablation procedures. The Investigator shall describe risks in further detail when asked by the subject. The risks must be continuously monitored, assessed and documented by the Investigator. Possible additional risks for participating the study include the following (although others are possible) and are further defined in Appendix F.

- Anemia-deficiency of red blood cells or of hemoglobin in the blood resulting in weariness.
- Anxiety-a feeling of worry, nervousness, or unease.
- Back pain- pain felt in the lower or upper back.
- Bleeding e.g. bleeding into the retroperitoneal space.
- Bronchitis, cough, pneumonia-inflammation of the lungs can be caused by a virus or bacteria.
- Cardiac tamponade-pressure on the heart as a result of fluid collecting in the sac surrounding the heart.
- Cardiopulmonary arrest-cessation of blood circulation and/or respiration due to dysfunction of the heart and/or lungs.
- Chest discomfort/pain/pressure-includes a range of feeling from sharp stabbing to dull ache in the chest.
- Cold feeling-having a low or inadequate temperature.
- Complications associated with contrast agents-adverse effects of contrast agents used during the procedure (e.g. allergic reaction or radio contrast nephropathy).
- Complications associated with medications commonly utilized during the procedure-known risks of medications commonly used during the procedure (e.g. narcotics, anxiolytics, other pain medications, anti-vasospasm agents).
- Complications at catheter insertion site in the groin:
 - AV fistula-an abnormal connection between an artery and a vein (i.e., cause by needle insertion through the femoral artery and vein).
 - Hematoma/Bruising-a collection of blood in the tissue surrounding the catheter insertion site.
 - Infection-localized redness, heat swelling and pain at the catheter insertion site.

- Pain-discomfort at the catheter insertion site that can range from mild to severe.
- Pseudoaneurysm-a collection of blood in the tissue surrounding the catheter insertion site due to ongoing leaking of blood from a blood vessel.
- Significant bleeding-blood loss from the catheter insertion site requiring surgery or transfusion of 2 or more units of packed red blood cells (PRBCs).
- Coronary artery spasm, vasospasm-constriction of a blood vessel.
- Death-a complication or deterioration of health ultimately leading to a patient's death.
- Dissection of a blood vessel-a tear within the wall of a blood vessel.
- Dizziness, lightheadedness-feeling faint, woozy, weak or unsteady.
- Embolism-formation and dislodgement of a blood clot (thrombus) or dislodgement of cholesterol/plaque within the blood vessel, which travels downstream into small vessels, blocking blood flow and causing temporary or permanent damage to organs distal to blockage. Emboli are known to cause myocardial infarction, transient ischemic attack, stroke/cardiovascular accident, blurred vision, visual changes, paralysis, paresis, or kidney damage, peripheral ischemia and may ultimately lead to incapacitation or death. Symptomatic and non-symptomatic.
- Endocarditis –inflammation of the inner surface of the heart.
- Esophageal injury –damage to your swallowing tube, atrio-esophageal fistula - abnormal passageway between the heart and esophagus, hematemesis (vomiting blood).
- Fatigue- extreme tiredness.
- Fever- abnormally high body temperature.
- Gastroparesis- delayed gastric emptying.
- Headache- pain in the head.
- Heartblock requiring permanent pacemaker implantation
- Heart rhythm disturbances-disruption of normal heart rate or rhythm (e.g. atrial flutter, tachycardia, bradycardia).
- Hemothorax –collection of blood around the lungs.
- Hiccups- involuntary spasm of the diaphragm and respiratory organs.
- Hypertension-high blood pressure.
- Hypotension-low blood pressure.
- Infection (e.g. sepsis)
- Injury to lung- (e.g. bronchial lesion, hemoptysis, constriction, pulmonary hemorrhage, bronchia fistula).
- Mild skin discomfort or irritation-redness sensitivity of the skin cause during or after the procedures (e.g. electrodes used with the ECG and Holter recorder might cause mild skin discomfort or irritation or some skin discomfort following electrode removal or tape removal).
- Nausea-a sensation of unease and discomfort in the upper stomach with an urge to vomit.

- Perforation of a blood vessel or cardiac tissue-unintended puncture through the wall of a blood vessel or cardiac tissue.
- Pericardial effusion- fluid collecting in the sac that surrounds the heart.
- Pericarditis –inflammation of the sac that surrounds the heart.
- Phrenic nerve injury –damage to the nerve that controls breathing.
- Pleural effusion –collection of extra fluid around the lungs.
- Pneumothorax – collapsed lung.Pulmonary edema- excess fluid in the lungs.
- Pulmonary hypertension- high blood pressure that affects the arteries in the lungs and the right side of the heart.Pulmonary vein hematoma- trauma to the pulmonary vein.
- Pulmonary vein stenosis –blockage in the blood vessels takes blood from the lungs to the heart.
- Renal dysfunction-kidneys fail to adequately filter waste products from the blood.
- Right sided heart failure- right side of the heart is not pumping blood to the lung normally.
- Shivering- body shaking.
- Shortness of breath- difficulty breathing.
- Small ischemic cerebral (brain) lesions not accompanied by clinically apparent symptoms have been found on brain imaging performed after an AF ablation procedure. So far, the relationship between these lesions and an increased incidence of stroke or transient ischemic attack (a mini stroke) has not been established. However, whether these lesions will result in long term cognitive decline (e.g. loss of memory and trouble thinking) is unclear.
- ST elevation- the ST segment of an ECG is abnormally high above the baseline.
- Sore throat- pain in the throat.
- Urinary infection- an infection in the urinary system.
- Vascular complications requiring surgery-damage to an artery (e.g. femoral) or vein requiring surgical repair.
- Vasovagal reaction- reflex of the involuntary nervous system that causes the heart to slow down and blood pressure drops.
- Vomiting-forceful expulsion of stomach contents through the mouth and/or nose.

The risks of participating in this clinical study are the same as the cryoablation procedure risks, and also include:

- Risks/discomforts associated with sedation/anesthesia:
 - Hoarseness.
 - Myalgia (pain in the muscles).
 - Numbness and tingling of the fingers.
 - Diarrhea.
 - Dry mouth.
 - Sleepiness.

- Radiation exposure due to potential for additional CT/MRI scan or Chest X-rays.
- Patches and adhesive used with the ambulatory monitoring equipment may cause skin discomfort or irritation, or some skin discomfort following patch removal.

